5.1.2 Trial Endpoints

5.1.2.1 Primary Endpoints

For Part A, the primary endpoint is the confirmed BOR for each subject, per RECIST 1.1, as determined by the IERC (see Section 7.3).

For Part B, the primary endpoint is durable response, defined as objective response (CR or PR) according to RECIST 1.1, determined by an IERC, with a duration of at least 6 months.

5.1.2.2 Secondary Endpoints and Exploratory Endpoints

Part A: Secondary endpoints include:

- duration of response according to RECIST 1.1 as determined by an IERC,
- PFS time according to RECIST 1.1 as determined by an IERC,
- occurrence, number, and severity of treatment-related AEs according to NCI-CTCAE v 4.0, clinical laboratory assessments, vital signs, and ECG parameters,
- OS time,
- response status according to RECIST 1.1 at 6 and 12 months after start of study treatment,
- serum titers of anti-avelumab antibodies, and
- population PK profile of avelumab (sparse sampling).

Part A: Exploratory endpoints include:

CCI

Part B: Secondary endpoints include:

- OS time,
- confirmed BOR per RECIST 1.1 as determined by an IERC,
- duration of response according to RECIST 1.1 as determined by an IERC,
- PFS time according to RECIST 1.1 as determined by an IERC,
- occurrence and severity of treatment-related AEs according to NCI-CTCAE v 4.0,
- response status according to RECIST 1.1 at 6 and 12 months after start of study treatment,
- serum titers of anti-avelumab antibodies, and
- population PK profile of avelumab (sparse sampling).

Part B: Exploratory endpoints include:

CCI

5.1.3 Trial Medication Administration and Schedule

Subjects will receive IV infusion of avelumab (10 mg/kg over 1 hour [-10 minutes / +20 minutes, that is, over 50 to 80 minutes]) once every 2 weeks (one treatment cycle). The trial treatment schedule is illustrated in [Appendix I](#). In order to mitigate infusion-related reactions, a premedication regimen of antihistamine (diphenhydramine or equivalent) and paracetamol (acetaminophen, IV or oral equivalent) is required prior to the first 4 infusions of avelumab. Premedication should be administered for subsequent avelumab doses based upon clinical judgment and presence / severity of prior infusion reactions. This regimen may be modified based on local treatment standards and guidelines as appropriate. Steroids as premedication are not acceptable.

The formulation and packaging information of avelumab is provided in Sections [6.1](#) and [6.6](#), respectively.

5.1.4 Dose Modification and Adverse Drug Reactions Requiring Treatment Discontinuation

5.1.4.1 Dose Modification

The dose of avelumab will be calculated based on the weight of the subject determined on the day of (for Part A), or within 3 days of each drug administration (Part B).

Each subject will stay on the avelumab assigned dose of 10 mg/kg unless treatment needs to be stopped. Dosing modifications (changes in infusion rate) and dose delays are described in Section [5.1.4.2](#). There are to be no dose reductions.

5.1.4.2 Adverse Drug Reactions Requiring Treatment Discontinuation or Modifications

The following ADRs require permanent treatment discontinuation of avelumab:

Any Grade 4 ADRs require treatment discontinuation with avelumab except for single laboratory values out of normal range that are unlikely related to trial treatment as assessed by the Investigator, do not have any clinical correlate, and resolve within 7 days with adequate medical management.

Any Grade 3 ADRs require treatment discontinuation with avelumab except for any of the following:

- Transient (≤ 6 hours) Grade 3 flu-like symptoms or fever, which is controlled with medical management
- Transient (≤ 24 hours) Grade 3 fatigue, local reactions, headache, nausea, emesis that resolves to Grade ≤ 1

- Single laboratory values out of normal range (excluding Grade ≥ 3 liver function test increase) that are unlikely related to trial treatment according to the Investigator, do not have any clinical correlate, and resolve to Grade ≤ 1 within 7 days with adequate medical management
- Tumor flare phenomenon defined as local pain, irritation, or rash localized at sites of known or suspected tumor
- Change in Eastern Cooperative Oncology Group Performance Status (ECOG PS) to ≥ 3 that does not resolve to ≤ 2 within 14 days (infusions should not be given on the following cycle, if the ECOG PS is ≥ 3 on the day of study drug administration)
- Asymptomatic Grade ≥ 3 lipase or amylase elevation not associated with clinical manifestations of pancreatitis. Medical Monitor must be consulted for such lipase and amylase abnormalities.

Any Grade 2 ADR should be managed as follows:

- Infusion should not be given in case of ongoing Grade 2 ADR on the day of study treatment administration.
- Treatment can be resumed according to the original schedule once the ADR has resolved to Grade ≤ 1 . Up to 2 subsequent study drug may be omitted. If more than 2 doses are skipped, treatment may be resumed after consultation with the Medical Monitor.

Infusion-related reactions, hypersensitivity reactions (Grades 1 to 4), tumor lysis syndrome, and irAEs should be handled according to guidelines in Sections 6.5.4.1, 6.5.4.2, 6.5.4.3, and 6.5.4.4, respectively.

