5.5.3 Withdrawal from the Investigational Medicinal Product

The subject must be withdrawn in the event of any of the following:

- Therapeutic failure as outlined in Section 5.5.1
- Occurrence of an exclusion criterion, which is clinically relevant and affects the subject's safety, if discontinuation is considered necessary by the Investigator and/or Sponsor
- Therapeutic failure requiring urgent additional drug (if applicable)
- Occurrence of any Grade ≥ 3 ADRs as defined in Section 5.1.4.2
- Occurrence of AEs, resulting in the discontinuation of the study drug being desired or considered necessary by the Investigator and/or the subject
- Occurrence of pregnancy
- Use of a nonpermitted concomitant drug, as defined in Section 6.5.2, where the predefined consequence is withdrawal from the study drug

- Noncompliance (see Section 6.9)

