
Grade 3 to 4
 
Grade 3: Severe new symptoms; New / worsening hypoxia;
 
Grade 4: life-threatening
	
Discontinue avelumab therapy
 
Hospitalize
 
Pulmonary and Infectious Disease consults
 
1.0 to 2.0 mg/kg/day prednisone or equivalent
 
Add prophylactic antibiotics for opportunistic infections
 
Consider bronchoscopy, lung biopsy
	
If improves to Grade \leq 1:
 
Taper steroids over at least 1 month
 
If not improving after 48 hours or worsening:
 
Add additional immunosuppression (for example, infliximab, cyclophosphamide, IV immunoglobulin, or mycophenolate mofetil)

Hepatic irAEs		
Grade of Liver Test Elevation (NCI-CTCAE v4)	Management	Follow-up

Grade 1
 
Grade 1 AST or ALT $>$ ULN to $3.0 \times$ ULN and / or total bilirubin $>$ ULN to $1.5 \times$ ULN
	
Continue avelumab therapy
	
Continue liver function monitoring
 
If worsens:
 
Treat as Grade 2 or 3 to 4

Grade 2
 
AST or ALT $>$ 3.0 to $\leq 5 \times$ ULN and / or total bilirubin $>$ 1.5 to $\leq 3 \times$ ULN
	
Delay avelumab therapy
 
Increase frequency of monitoring to every 3 days
	
If returns to Grade \leq 1:
 
Resume routine monitoring, resume avelumab therapy
 
If elevations persist $>$ 5 to 7 days or worsen:
 
Treat as Grade 3 to 4

Grade 3 to 4
 
AST or ALT $>$ $5 \times$ ULN and / or total bilirubin $>$ $3 \times$ ULN
	
Discontinue avelumab therapy
 
Increase frequency of monitoring to every 1 to 2 days
 
1.0 to 2.0 mg/kg/day prednisone or equivalent
 
Add prophylactic antibiotics for opportunistic infections
 
Consult gastroenterologist / hepatologist
 
Consider obtaining MRI/CT scan of liver and liver biopsy if clinically warranted (for trial sites in Germany, only MRI is to be used)
	
If returns to Grade \leq 1:
 
Taper steroids over at least 1 month
 
If does not improve in $>$ 3 to 5 days, worsens or rebounds:
 
Add mycophenolate mofetil 1 gram (g) twice daily
 
If no response within an additional 3 to 5 days, consider other immunosuppressants per local guidelines

Renal irAEs		
Grade of Creatinine Increased (NCI-CTCAE v4)	Management	Follow-up
Grade 1 Creatinine increased > ULN to 1.5 × ULN	Continue avelumab therapy	Continue renal function monitoring If worsens: Treat as Grade 2 to 3 or 4.

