Immune-related myocarditis	
Permanently discontinue avelumab.
 
Guideline based supportive treatment as appropriate as per cardiology consult.^a
 
1.0 to 2.0 mg/kg/day prednisone or equivalent
 
Add prophylactic antibiotics for opportunistic infections.
	
Once improving, taper steroids over at least 1 month
 
If no improvement or worsening, consider additional immunosuppressants (e.g. azathioprine, cyclosporine A)

a Local guidelines, or eg, European Society of Cardiology or American Heart Association guidelines. European Society of Cardiology guidelines website: https://www.escardio.org/Guidelines/Clinical-Practice-Guidelines American Heart Association guidelines website: http://professional.heart.org/professional/GuidelinesStatements/searchresults.jsp?q=&y=&t=1001
		
Other irAEs (not described above)		
Grade of other irAEs (NCI-CTCAE v4)	Initial Management	Follow-up Management
Grade 2 or Grade 3 clinical signs or symptoms suggestive of a potential irAE	Withhold avelumab therapy pending clinical investigation	
If irAE is ruled out, manage as appropriate according to the diagnosis and consider re-starting avelumab therapy
 
If irAE is confirmed, treat as Grade 2 or 3 irAE.

Grade 2 irAE or first occurrence of Grade 3 irAE	
Withhold avelumab therapy
 
1.0 to 2.0 mg/kg/day prednisone or equivalent
	
If improves to Grade \leq 1:
 
Taper steroids over at least 1 month and resume avelumab therapy following steroids taper.

	Add prophylactic antibiotics for opportunistic infections Specialty consult as appropriate	
Recurrence of same Grade 3 irAEs	Permanently discontinue avelumab therapy 1.0 to 2.0 mg/kg/day prednisone or equivalent Add prophylactic antibiotics for opportunistic infections Specialty consult as appropriate	If improves to Grade \leq 1: Taper steroids over at least 1 month.
Grade 4	Permanently discontinue avelumab therapy 1.0 to 2.0 mg/kg/day prednisone or equivalent and/or other immunosuppressant as needed Add prophylactic antibiotics for opportunistic infections Specialty consult.	If improves to Grade \leq 1: Taper steroids over at least 1 month
Requirement for 10 mg per day or greater prednisone or equivalent for more than 12 weeks for reasons other than hormonal replacement for adrenal insufficiency Persistent Grade 2 or 3 irAE lasting 12 weeks or longer	Permanently discontinue avelumab therapy Specialty consult	

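### In Protocol 5.1.4.2 the Grade 4 laboratory exception omits the liver-test exclusion found at Grade 3, so an isolated liver-test reaction must stop avelumab at Grade 3 but may continue at Grade 4

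*Protocol*

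**What the plan says.** Protocol 5.1.4.2 has two separate stop rules for ADRs.

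At Grade 4 the rule is: "Any Grade 4 ADRs require treatment discontinuation with avelumab except for single laboratory values out of normal range that are unlikely related" to treatment as the Investigator sees it. The same sentence adds two further conditions: no clinical correlate, and resolution within 7 days.

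At Grade 3, discontinuation is again required, with a bulleted list of exceptions. One bullet is the laboratory exception: "Single laboratory values out of normal range (excluding Grade ≥ 3 liver function test increase", after which the bracket closes. Its other conditions match those at Grade 4, except that resolution must be to Grade 1 or lower. The last bullet exempts an asymptomatic "lipase or amylase elevation not associated with clinical manifestations of pancreatitis". It gives the grade with a ≥ 3 sign, sets no relatedness or time condition, and adds "Medical Monitor must be consulted for such lipase and amylase abnormalities".

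The section ends by routing infusion reactions, hypersensitivity, "tumor lysis syndrome, and irAEs should be handled according to guidelines in Sections" 6.5.4.1 to 6.5.4.4. In Table 5 of 6.5.4.4, the Grade 3 to 4 hepatic row says "Discontinue avelumab therapy" and the Grade 4 row for other immune-related events says "Permanently discontinue avelumab therapy 1.0 to 2.0 mg/kg/day prednisone or equivalent and/or other immunosuppressant as needed". Section 5.5.3 makes withdrawal mandatory for Grade ≥ 3 "ADRs as defined in Section 5.1.4.2". Section 7.4.1.1 defines an ADR as an adverse event that the Investigator, the Sponsor or both suspect is related to avelumab.

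**The concern.** A mandatory stop rule should not become looser as severity rises. Here the Grade 3 text singles out liver tests as not excusable, while the Grade 4 text is silent. Dose reduction is not allowed (Protocol 5.1.4.1), so these rules decide whether a subject comes off avelumab for good.

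The lipase/amylase bullet raises a related doubt. Its grade sign reaches Grade 4, but the bullet sits under the Grade 3 rule, and nothing says which line governs.

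At stake are consistent safety decisions across sites and, secondarily, the coding of deviations. Both SAPs list continuing after a Grade 4 ADR as an important deviation (PDEV14; Part A SAP Appendix II, Part B SAP Appendix I). Neither states any exemption, and both leave the case to medical review against the same protocol text.

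**Working it through.** No arithmetic applies. The check sets the two rules side by side and runs test cases through them.

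**Step 1, scope.** Events handled as immune-related leave 5.1.4.2 for Table 5. That table stops avelumab for Grade 3 to 4 hepatic events and for other Grade 4 events, so those cases are settled. What remains is ADRs not handled that way.

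**Step 2, the two laboratory exceptions.**

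| Condition | Grade 3 exception | Grade 4 exception |
|---|---|---|
| Single laboratory value | yes | yes |
| Investigator judges it unlikely related | yes | yes |
| No clinical correlate | yes | yes |
| Resolution within 7 days | to Grade ≤ 1 | stated without a grade |
| Liver-test increase excluded | yes | not stated |

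**Step 3, liver-test case.** Take an isolated ALT rise that the Investigator judges unlikely related and the Sponsor suspects (so it is an ADR under 7.4.1.1), with no clinical correlate and back to Grade 1 or lower within 7 days.
- At Grade 3, the laboratory bullet excludes it. The other bullets (transient flu-like symptoms or fever; transient fatigue and similar; tumor flare; performance status; lipase or amylase) do not cover it. Result: stop.
- At Grade 4, every stated condition of the exception is met and no exclusion applies. Result: continuation is permitted.

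**Step 4, does other text close the gap?** Section 5.5.3 refers back to 5.1.4.2. Table 5 closes it only if the event is handled as immune-related. Neither settles the case in Step 3.

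**Step 5, lipase/amylase case.** Take an asymptomatic Grade 4 lipase rise, not handled as immune-related, that fails the Grade 4 exception because it is judged related or lasts more than 7 days.
- If the bullet is read under its Grade 3 stem, it can lift only the Grade 3 rule. Grade 4 stops, and the ≥ sign is an error.
- If the bullet is read literally, Grade 4 is exempt after Medical Monitor consultation, contrary to the Grade 4 sentence.

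For the first reading: each rule has its own exception, and the liver exclusion in the same list also uses ≥ 3 where the sign can do nothing. For the second: the first two bullets of the list say plain Grade 3, so the change of sign could be deliberate. No precedence is stated.

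**The case against.** The strongest reply on the liver-test point is how much must coincide: a single Grade 4 liver value, no clinical correlate, resolution in 7 days, suspicion by the Sponsor but not the Investigator, and nobody handling it as a hepatic immune-related event. The Grade 3 to 4 hepatic row of Table 5 is defined by laboratory thresholds alone (AST or ALT above 5 × ULN, bilirubin above 3 × ULN, or both), so a suspected Grade 4 rise would ordinarily be assessed there. The exception also only permits continuation; 5.5.3 lets the Investigator or the subject stop for any adverse event. All of this stands and limits the point to a corner. It does not correct the text, because Table 5 applies only once the event is treated as immune-related.

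On lipase/amylase, the reply is that the stem settles the matter and Grade 4 stops. That is a coherent reading, and it is why confidence here is only moderate. Even so, the sign misleads a site reading a mandatory stop rule. The required Medical Monitor consultation limits the practical risk, but the bullet does not say what the consultation may decide.

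A reader might infer two stronger claims. One is that the protocol flatly contradicts itself on Grade 4 lipase or amylase; the stem reading prevents that conclusion. The other is that severe liver toxicity is in general treated more leniently than moderate toxicity; Table 5 and the conditions of the exception rule that out.

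**Conclusion.** The point holds in a narrow form and is minor. As written, the Grade 4 laboratory exception lacks an exclusion that the Grade 3 exception has, and in the case in Step 3 the more severe event gets the more permissive rule. This rests on two assumptions: that the event is not handled under 6.5.4.4, and that an Investigator's judgement of unlikely related means the Investigator does not suspect avelumab, so that only Sponsor suspicion makes it an ADR. The lipase/amylase wording is a secondary ambiguity.

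The number of subjects affected cannot be estimated. The readable blood chemistry text in Protocol 3.4 reports Grade 3 or 4 AST increases in 30 subjects (6.3%) in the dose expansion phase. It does not split Grade 3 from Grade 4 or give relatedness or duration, so it does not size this corner. That the set is small follows from the conditions that must coincide, not from a rate.

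No efficacy estimate, alpha or power figure changes. Continuing after a Grade 4 ADR is not a criterion for the per-protocol set in Section 10 of either SAP.

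**What to change.** In Protocol 5.1.4.2:

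1. Add *(excluding liver function test increase)* to the Grade 4 laboratory exception.
2. Change the lipase/amylase bullet to *Grade 3*. If Grade 4 was meant to be exempt, instead repeat the exception under the Grade 4 sentence with mandatory Medical Monitor consultation. The choice belongs to the sponsor's medical team.

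The cost is a few words at the next amendment or in a clarification letter, with no new data, visits or subjects. The change helps only subjects still on treatment. The medical review of PDEV14 should then follow the clarified wording.

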- therapeutic failure (subjects may stay on treatment beyond observation of progressive disease [PD] provided there is no significant clinical deterioration);
- unacceptable toxicity; or
- any criterion for withdrawal from the trial or the study drug is fulfilled.

Significant clinical deterioration is defined as

- new symptoms or worsening of symptoms that cannot be managed by optimal supportive care or disease localization that require immediate medical or surgical intervention (for example, lesion close to the spine), and/or
- change in Eastern Cooperative Oncology Group Performance Status (ECOG PS) to ≥ 3 that lasts more than 14 days.

Decisions regarding medical management of subjects will be made by the Investigator; however, the primary and secondary endpoint determinations will be according to tumor assessments performed by the IERC.

The date of the first observation of PD by RECIST 1.1 by the IERC will be used to determine the date of the PD as well as the duration of response in all subjects, including the subjects for which treatment was maintained beyond first determination of disease progression.

Adverse events will be assessed throughout the trial period and evaluated using the National Cancer Institute (NCI) Common Technology Criteria version 4.0 (CTCAE v 4.0).

Health-related quality of life will be assessed using a generic instrument (EuroQol EQ-5D [EQ-5D]), a cancer-specific instrument including a melanoma-specific module (Functional Assessment of Cancer Therapy – Melanoma [FACT-M]), and subject interviews (optional).

In Part A there will be 1 interim analysis for futility after 20 subjects have been enrolled and observed for at least

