	(according to NCI-CTCAE v 4.0). Following avelumab infusions, subjects should be observed based upon clinical judgment and presence / severity of prior infusion reactions. In the case of Grade 1 or 2 infusion reactions, the infusion rate should be decreased by 50%.
Reference therapy: dose / mode of administration/dosing schedule	Not applicable.
Planned treatment duration per subject	
Subjects will receive avelumab treatment until significant clinical deterioration, unacceptable toxicity, or any criterion for withdrawal from the trial or study drug is fulfilled.
 
For Part A: Subjects who have experienced a confirmed complete response (CR) should be treated for a maximum of 12 months and a minimum of 6 months after confirmation, at the discretion of the Investigator. If the Investigator believes that a subject may benefit from treatment beyond 12 months, it may be permissible after discussion with the sponsor. Part B: Subjects who have experienced a confirmed CR should be treated for a minimum of 12 months after confirmation, at the discretion of the Investigator. If the Investigator believes that a subject may benefit from treatment beyond 12 months, it may be permissible after discussion with the sponsor. For both Part A and Part B, in case a subject with a confirmed CR relapses after stopping treatment, but prior to the end of the trial, 1 re-initiation of treatment is allowed at the discretion of the Investigator and agreement of the trial Medical Monitor. In order to be eligible for retreatment, the subject must not have experienced any toxicity that led to treatment discontinuation of the initial avelumab therapy. Subjects who re-initiate treatment will stay on study and will be treated and monitored according to the protocol and the “until progression” schedule in the Schedule of Assessments.

Primary endpoint	
Part A: The primary endpoint for the trial is the confirmed BOR, per RECIST 1.1, as determined by an IERC.
 
Both CR and partial response (PR) must be confirmed by a second tumor assessment that will be performed preferably at the regularly scheduled 6-week assessment interval, but no sooner than 5 weeks after the initial documentation of CR or PR.

	
Part B: The primary endpoint is durable response, defined as objective response (CR or PR) according to RECIST 1.1, determined by an IERC, with a duration of at least 6 months.

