The decision to continue treatment should be discussed with the Medical Monitor and documented in the trial records.

Subjects who experience significant clinical deterioration, as defined above, in the absence of confirmed PD should be discontinued from further treatment with avelumab.

The treatment with avelumab should be stopped immediately, if the subject does not tolerate avelumab anymore or if therapeutic failures occur, which requires urgent additional drug or results in clinical progression/deterioration.

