| Subjects that developed withdrawal criteria whilst on the study but were not withdrawn; | Other Criteria | Subject became pregnant, but continued on the study. | PDEV12 | | Section 5.5.2 | |
| Subjects who developed withdrawal criteria whilst on the study but were not withdrawn; | Other Criteria | Subjects received treatment despite confirmed progression and significant clinical deterioration. Subjects had ECOG \geq 3, did not resolved to \leq 2 by day 14 of next cycle, and continued on the study. | PDEV13 | | Section 5.5.2 and 5.5.3 | Medical review required |
| Subjects who developed withdrawal criteria whilst on the study but were not withdrawn; | Other Criteria | Subject developed grade 4 ADR, but continued on the study. | PDEV14 | | Section 5.5.2 and 5.5.3 | Medical review required |
| Subjects who developed withdrawal criteria whilst on the study but were not withdrawn; | Other Criteria | Subject developed grade 3 ADR, but continued on the study. | PDEV15 | | Section 5.1.4.2 | Medical review required |
| Subjects dosing error (\geq +/- 10 % assigned dose) | Other | Dosing error | PDEV16 | | Section 6.2 | List if relative dose intensity \geq 1.10 or \leq 0.90 |
| Subjects on avelumab treatment did not receive premedication | IP compliance | Subjects on avelumab treatment did not take mandatory premedication | PDEV17 | | Section 6.2 | Medical review required |

MSB0010718C MSB0010718C in Merkel Cell Carcinoma
EMR100070-003 Part B

| | Category of Protocol Deviation | Description of Protocol Deviation | Deviation Code | Clinically Important | Protocol Section | Proposed check / comment |
|---|---------------------------------------|--|-----------------------|-----------------------------|-------------------------|---------------------------------|
| Any other protocol deviation which is deemed to be significant but has not been pre-specified in this table | any | any | PDEV99 | | NA | Medical review required |

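### Protocol 5.1.4.2 exempts a drug-related ECOG PS of 3 or more that persists past 14 days from the Grade 3 discontinuation rule, while the synopsis and 5.5.1 treat that state as ending treatment

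*Protocol*

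**What the plan says.** **Protocol 5.1.4.2.** The Grade 3 rule opens: "Any Grade 3 ADRs require treatment discontinuation with avelumab except for any of the following". The fifth item in that list is "Change in Eastern Cooperative Oncology Group Performance Status (ECOG PS) to" 3 or more that fails to return to 2 or less within 14 days. A parenthesis in the same item adds that "infusions should not be given on the following cycle" if ECOG PS is 3 or more on the day of dosing.

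**Protocol synopsis.** Under trial design, a list headed "Significant clinical deterioration is defined as" includes a "change in Eastern Cooperative Oncology Group Performance Status (ECOG PS) to" 3 or more for longer than 14 days. Under planned treatment duration: "Subjects will receive avelumab treatment until significant clinical deterioration", with toxicity and the other withdrawal criteria as further end points.

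**Protocol 5.5.1.** Absence of the same ECOG change is among the terms for continuing after a first observation of progression. The section then says: "Subjects who experience significant clinical deterioration, as defined above, in the absence of confirmed PD should be discontinued from further treatment with avelumab".

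**Protocol 5.5.3.** Therapeutic failure under 5.5.1 and Grade 3 or higher reactions under 5.1.4.2 are separate items in one list, any of which requires withdrawal from study drug.

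**SAPs.** PDEV13 (Part A SAP, Appendix II; Part B SAP, Appendix I) is filed under subjects who met withdrawal criteria but were not withdrawn. Its first sentence reads "Subjects received treatment despite confirmed progression and significant clinical deterioration". Its second concerns subjects whose ECOG PS reached 3 or more, had not come down to 2 or less by day 14 of the next cycle, and who stayed on study.

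**The concern.** One clinical state is an exception to stopping in one section and part of the definition of a reason to stop in others. A site working from 5.1.4.2 can hold a subject on study with the infusion withheld. A site working from 5.5.1 would end treatment. The first site may then appear in the deviation listing for following a section of the protocol. With approximately 60 sites planned, uneven handling is a realistic prospect. The rule also concerns subjects in poor condition with a suspected drug reaction, so the first issue is safety. Time on treatment and the deviation listings come second.

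**Working it through.** No figure in the plan depends on this point, so the check sets the passages side by side.

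**Step 1. Is it the same state?**

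| Place | State | Clock | Consequence |
|---|---|---|---|
| Protocol 5.1.4.2 | ECOG PS 3 or more, not back to 2 or less | 14 days | Exempt from the Grade 3 rule; next cycle's infusion withheld if still 3 or more on the dosing day |
| Synopsis | ECOG PS 3 or more | More than 14 days | Treatment ends |
| Protocol 5.5.1 | ECOG PS 3 or more | More than 14 days | Discontinue, even without confirmed progression |
| PDEV13, second sentence | ECOG PS 3 or more, not back to 2 or less | Day 14 of the next cycle | Withdrawal criterion not acted on |

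The first three rows describe one state: ECOG PS of 3 or more still present after 14 days.

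**Step 2. Which subjects meet both rules?** Section 5.1.4.2 covers adverse drug reactions, which 7.4.1.1 defines as adverse events suspected to be related to avelumab. The exception list belongs to the Grade 3 rule. The overlap is therefore the set of declines handled as drug-related Grade 3 events.

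**Step 3. Does the list explain the item?** The other three time-limited exceptions cover events that are transient or resolve (6 hours, 24 hours, 7 days). This one is defined by failure to resolve. Read literally, a drug-related Grade 3 decline that recovers within 14 days is not covered by this exception, and one that does not recover is. The wording may not say what was meant, but the documents do not settle that.

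**Step 4. Is there an order of precedence?** Section 5.5.3 names both routes. Neither it nor any other section says whether the 5.1.4.2 exception yields to 5.5.1 when both apply.

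**Step 5. How far apart are the clocks?** A cycle is 2 weeks, or 14 days. Suppose the change begins on day d of a cycle, dosing is on schedule, and the next cycle means the one after onset. Day 14 of the next cycle then falls 14 + 14 − d = 28 − d days later. For d = 14 that is 14 days; for d = 1 it is 27 days. PDEV13 can therefore allow up to 27 − 14 = 13 days more than the 14 days in 5.1.4.2.

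**Step 6. Two hypothetical subjects,** each with a drug-related Grade 3 decline starting on day 1.

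- *ECOG PS 3 through day 21, then 2 from day 22.* The day 15 infusion is withheld. The exception in 5.1.4.2 does not require discontinuation, and its parenthesis speaks only of the following cycle. The synopsis and 5.5.1 criterion was met once 14 days had passed. The ECOG sentence of PDEV13 records nothing, because ECOG PS is 2 on day 28.
- *ECOG PS still 3 on day 28, subject kept on study with the infusion withheld.* This is consistent with 5.1.4.2 read alone, contrary to 5.5.1, and recorded under PDEV13.

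The Part B SAP also has PDEV15 for continuing after a Grade 3 reaction, citing 5.1.4.2. It does not say whether subjects covered by the exception are left out.

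**The case against.** The strongest reply is that an exception to one stopping rule is not permission to continue. Section 5.5.3 requires withdrawal if any listed criterion is met, and 5.5.1 is on that list in its own right. A careful site would stop the subject under 5.5.1 whatever 5.1.4.2 says. This is a fair reading and it lowers the risk. It does not remove the conflict, because a reader must supply a precedence rule that the text does not state.

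Other points stand and limit the finding:

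- **Reach.** A reader might infer that every subject with persistent ECOG PS of 3 or more is affected. The documents do not support that. A decline attributed to disease is not an adverse drug reaction and falls under 5.5.1 alone.
- **Dosing.** A reader might infer that 5.1.4.2 lets a subject be dosed at ECOG PS 3 or more, or that sites could act in opposite ways. The parenthesis withholds the following cycle's infusion in that condition. The gap is between withholding and permanent discontinuation, including what follows a later recovery.
- **PDEV13.** Its first sentence needs confirmed progression as well as deterioration, so it is not evidence here; only the second sentence is. The entry cites Sections 5.5.2 and 5.5.3, and the appendices refer to protocol versions 7.0 (Part A) and 11.0 (Part B), both before Amendment 11. It requires medical review, and Part B does not mark it as clinically important.

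**Conclusion.** The contradiction is real and stands in the current protocol text, so the plan is wrong as written on this point. For declines handled as drug-related Grade 3 events, 5.1.4.2 withholds where the synopsis and 5.5.1 discontinue, and PDEV13 applies a third clock. The documents do not say how many subjects this would involve.

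It matters for patient safety, consistency across sites and the deviation listings, and possibly for exposure summaries. A reader might infer an effect on the efficacy results. The documents do not support that: persistent ECOG PS of 3 or more is not a per-protocol criterion in either SAP, and no endpoint definition, censoring rule or error rate refers to it.

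The conclusion assumes that the ECOG item belongs to the exception list, as its place between tumor flare and lipase or amylase elevation indicates. It takes no position on which rule is clinically right.

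**What to change.** Reconcile Protocol 5.1.4.2, both synopsis passages (the definition of deterioration and the treatment duration), 5.5.1 and 5.5.3, so that one rule and one time threshold apply to ECOG PS of 3 or more that persists. State how the exception list in 5.1.4.2 relates to withdrawal under 5.5.1. Then align the second sentence of PDEV13 in both SAPs with that rule and its clock, and say in the Part B SAP whether PDEV15 applies to this state. The sponsor's clinical team must decide which rule holds.

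The cost is wording in the next protocol amendment and a short edit to each SAP's deviation appendix. No sample size or efficacy analysis changes. Deviations already classified under PDEV13 would need checking against the reconciled wording.
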